Study Description	This is a single-arm, 2-stage, phase II study of the safety and efficacy of daratumumab in combination with azacitidine and dexamethasone in relapsed/refractory multiple myeloma (RRMM) patients who have previously been exposed to daratumumab. Based on pre-clinical data we hypothesize that azacitidine, by upregulating the expression of CD38, can potentially increase the antibody-dependent cell-mediated cytotoxicity and efficacy of daratumumab on multiple myeloma cells and help reverse daratumumab resistance. This study aims to assess the efficacy and safety of daratumumab and azacitidine in relapsed refractory multiple myeloma.
Phase of Study	Phase 2
Investigational Products	Daratumumab and Azacitidine
Study population	Patients \geq 18 years of age with relapsed or refractory multiple myeloma (RRMM) who have progressed on \geq 2 lines of prior therapy, including an immunomodulatory drugs (IMiD) and proteasome inhibitor, and have previously been treated with daratumumab, with most recent daratumumab treatment being at least 6 months prior to enrollment to allow for CD38 normalization.
Primary Objective	
 To evaluate the efficacy, as determined by the overall response rate (ORR) of daratumumab in combination with azacitidine and dexamethasone in RRMM patients who have previously been exposed to daratumumab
Secondary Objectives	
 To evaluate duration of response per IMWG response criteria. To assess the safety and toxicity of azacitidine in combination with daratumumab and dexamethasone To assess the 1-year OS and PFS of daratumumab in combination with azacitidine and dexamethasone To evaluate the change in CD38 expression on plasma cells induced by azacitidine in patients with RRMM and correlate this change with depth and duration of response

Sample Size	
Simon's minimax two-stage design will be used.
 
The overall study (including the safety lead-in) plans to enroll 23 patients.
 
Safety Lead In: We expect to enroll 6 patients overall in the safety lead-in.
 
Stage 1: We expect to enroll a total of 13 patients during Stage 1 (including the 6 patients enrolled in the safety lead-in). Depending on the clinical response in Stage 1, Stage 2 will commence.
 
Stage 2: If there is ≥ 2 responses in 13 patients the study will enroll an additional 10 patients.
 
If there is ≤ 1 response in 13 patients the study will be stopped.

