6.1 Study Calendar

Period/ Procedure	Screening	Cycle 1 ^a (Pre- Induction Phase)	Cycle 1-2 ^a (Induction Phase)				Cycle 3 ^a (Consolidation Phase)				Cycle 4 ^a (Consolidation Phase)				Cycle 5-6 ^a (Consolidation Phase)				Cycle 7 ^a and Onwards (Maintenance Phase)	End of Treatment	Follow-up ^t	
Study Day/Visit Day	D -27 to D-8	D -7 to D-3	D1 (± 1 day)	D8 (± 1 day)	D15 (± 1 day)	D22 (± 1 day)	D1 (± 2 days)	D8 (± 2 days)	D15 (± 2 days)	D22 (± 2 days)	D1 (± 2 days)	D8 (± 2 days)	D15 (± 2 days)	D22 (± 2 days)	D1 (± 2 days)	D8 (± 2 days)	D15 (± 2 days)	D22 (± 2 days)	D1 (± 3 days)			
Study Treatment/Drug																						
Daratumumab ^b			x	x	x	x	x	x	x	x	x	x	x	x	x	x	x	x	x			
Azacitidine ^c		x				x			x				x		x		x		x			
Dexamethasone ^d			x	x	x	x	x	x	x	x	x	x	x	x	x	x	x	x	x			
Administrative Procedures																						
Informed Consent	x																			x		
Clinical Evaluation																						
Physical Exam	x	x	x				x				x				x				x			
Medical History	x																					
Vital signs	x	x	x	x	x	x	x	x	x	x	x	x	x	x	x	x	x	x	x	x		
Weight/height ^e	x	x	x	x	x	x	x	x	x	x	x	x	x	x	x	x	x	x	x	x		
Concomitant medications	x																					
AE assessment ^f	x																					
Performance status ^g	x	x	x				x				x				x				x			
Laboratory Assessments																						
Pregnancy Test ^h	x		x				x				x				x				x	x		
Type and Screen ⁱ	x																					
Hepatitis B (HBV) Serology ^j	x																					
HBV DNA Testing ^k	x																		x	x		
Blood	x	x	x	x	x	x	x	x	x	x	x	x	x	x	x	x	x	x	x	x		

Chemistry ^l																				
Hematology ^m	x	x	x	x	x	x	x		x	x	x		x	x	x	x	x	x	x	
Disease Evaluation^m																				
Immunoglobulin _{sⁿ}	x	x	x				x				x			x				x		
Serum M protein ^o	x	x	x				x				x			x				x		
sFLC ^p	x	x	x				x				x			x				x		
serum IFE ^q	x	x	x				x				x			x				x		
Urine M protein (24 hour urine) ^r	x																	x		
Skeletal Survey	Only as clinically indicated by standard of care																			
PET/CT/MRI	Only as clinically indicated by standard of care																			
Study Procedure/Correlative Studies																				
Bone Marrow Biopsy ^s	x		x																	

^a **Cycle:** Every cycle is 28 days (except for Cycle 1 which extends from day -7 to day 28). The treatment window is \pm 1 days for induction phase, \pm 2 days for consolidation phase, \pm 3 days for maintenance phase

^b **Daratumumab:** Daratumumab dose scheduling, pre-medications, dose modification, and DLTs are detailed in Section 5.

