8.2 Analyses

Analyses Population

Analysis of primary and secondary efficacy variables will be based on the response-evaluable population, which includes all subjects who have measurable disease and received at least 2 cycles of study treatment, and have at least 2 efficacy evaluation assessments. All safety analyses for AEs will be based on the safety analysis set, which includes all subjects who receive at least 1 cycle of study treatment.

Safety Analysis

The study will begin with accrual of 6 patients in a safety run-in with interim safety analysis occurring after these 6 patients have completed at minimum Cycle 1 and further accrual stopped until safety analysis completed. If $\geq 2/6$ patients in the safety cohort have dose limiting toxicities (DLTs) as defined in [Section 5.4](#), then further study accrual will be halted until the study PI, co-investigators, and the DSMC can review the data, and determine whether the study should continue, be amended with a lower starting dose of azacitidine, or be closed to further accrual. Toxicities will be monitored throughout the study using CTCAE 5.0 criteria. Though we do not expect to observe DLTs during the study period, formal safety bounds based upon monitoring DLTs as defined in [Section 5.4](#) will guide decisions about early stopping due to potential safety concerns. A Pocock-type sequential boundary⁵⁹ will be used to monitor dose-limiting toxicities with the aim of keeping the probability of early stopping at around 90% if the true underlying toxicity rate is 25%. If the number of dose-limiting toxicities is equal to or exceeds the stopping boundaries detailed in the following table at any point in the study, then accrual to the study will be suspended until the study PI, co-investigators, and the DSMC can review the data, and determine whether the study should continue, be amended with a lower starting dose of azacitidine, or be closed to further accrual. With a toxicity rate of 25%, the expected number of enrolled patients before stopping for excessive toxicities is 6.5.

Table 8-1. Table: Safety monitoring bounds for DLTs

Number of subjects	Stopping boundary
6-9	≥ 2
10-14	≥ 3
15-18	≥ 4
19-23	≥ 5

Adverse Events

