Secondary endpoints for efficacy will be assessed using duration of response (DOR), progression-free survival (PFS), and overall survival (OS). DOR is defined as the duration from the date of initial documentation of a response (PR or better) according to the IMWG criteria to the date of first documented evidence of progressive disease according to the IMWG criteria or death due to PD whichever occurred first. DOR for subjects who have not progressed will be censored at the last disease evaluation before the start of any subsequent anti-myeloma therapy. PFS which is defined as the duration from the date of first dose of study treatment to the date of first documented evidence of progressive disease or death, whichever occurs first. Participants without a disease assessment will be censored at the date of first study treatment received. OS will be calculated as the time from the first dose of study treatment until death from any cause. Participants who have not died will be censored at the last time the participant was known to be alive. Distributions of DOR, PFS, and OS will be summarized using the Kaplan-Meier estimator. For each secondary efficacy endpoint, median even-free survival will be reported and the corresponding 95% confidence interval will be calculated using Brookmeyer and Crowley method.

Correlative Studies Analysis

CD38 regulation by azacitidine (Secondary Endpoint)

Change in CD38 surface expression in MM patients treated with azacitidine will be summarized using descriptive statistics and tested using the one-sample t-test. Two-sided p-value less than 0.05 will be considered statistically significant. The proportion of patients with at least a 1.5 fold increase in CD38 expression after one cycle of azacitidine treatment will also be reported. This phase II sample size of 23 will provide >99% statistical power to detect a fold change of 1.965 (SD: 0.299) in CD38 surface expression of MM patients treated with azacitidine based on a one-sample t-test at a two-sided type I error rate of 0.05. This estimated change in CD38 surface expression was calculated from our preliminary pre-clinical data. The association between the fold change in CD38 expression post azacitidine treatment and depth of response and duration of response will also be evaluated using logistic regression, linear regression methods, and Spearman's correlation coefficient, as appropriate.

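### Section 8.2 analyses PFS and OS in a set that patients can enter only after about 5 to 9 weeks, but counts their time from first dose, so the earliest failures are left out

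*Combined protocol and SAP*

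**What the plan says.** Section 8.2 (Analyses Population) names one efficacy set: "Analysis of primary and secondary efficacy variables will be based on the response-evaluable population". To enter it a patient must have measurable disease and must have "received at least 2 cycles of study treatment, and have at least 2 efficacy evaluation assessments". The only other set defined is the safety set, which is for adverse events.

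Section 8.2 (Secondary endpoints for efficacy) lists DOR, PFS and OS. PFS runs from first dose to progression or death. For OS, "OS will be calculated as the time from the first dose of study treatment until death from any cause". Section 2.3 uses the same starting point for both.

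The censoring rules in Section 8.2 are:
- PFS: "Participants without a disease assessment will be censored at the date of first study treatment received".
- OS: "Participants who have not died will be censored at the last time the participant was known to be alive".
- DOR: "DOR for subjects who have not progressed will be censored at the last disease evaluation" that precedes any later anti-myeloma therapy.

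On timing, the Study Calendar (Section 6.1) makes every cycle 28 days, "except for Cycle 1 which extends from day -7 to day 28". Its disease-evaluation footnote places response assessment on Day 1 of each cycle from Cycle 2.

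The Abstract gives as a secondary objective: "To assess the 1-year OS and PFS of daratumumab in combination with azacitidine and dexamethasone".

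**The concern.** Entry to the analysis set depends on what happens after time zero. A patient must stay alive and on treatment for some weeks to be counted, yet those weeks are credited as event-free time. No landmark or delayed-entry adjustment is described, and no all-treated efficacy set exists.

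The loss is wider than early death. The set is defined by treatment received, so a patient who stops for toxicity in Cycle 1 is lost to OS even if death comes months later. A patient who progresses at the first assessment and stops is lost to PFS.

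The PFS censoring rule adds a contradiction. It provides for participants with no disease assessment, and a set requiring two assessments has none. Either the rule is idle or it was written for a wider set that the plan does not name.

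At stake are the 1-year and median estimates that a reader will compare with the poor background outcomes quoted in Sections 1.1 and 1.3.

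**Working it through.** **The plan's own figure.** The plan states no number for PFS or OS. Its only design figure, the Simon rule (at most 1 of 13 stops; at least 5 of 23 rejects; ORR 8% against 33%), reproduces with exact one-sided alpha 0.030 and power 0.903. It does not depend on the set used for PFS and OS.

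**Length of the window.** Cycle 1 lasts 7 + 28 = 35 days from the first azacitidine dose, and Cycle 2 ends at 35 + 28 = 63 days. The first two scheduled on-treatment assessments (Day 1 of Cycles 2 and 3) also fall at about days 35 and 63. So:
- If two cycles must be completed, or only on-treatment assessments count, the window is about 63 days (63/30.44 = 2.07 months).
- If starting Cycle 2 is enough, and a baseline or unscheduled assessment also counts, it is about 35 days (1.15 months).

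**Direction.** Suppose k of n patients have the event inside the window and are removed, with no early censoring. Later Kaplan-Meier values are then multiplied by n/(n − k), which exceeds 1.

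**A plain count.** Section 8.1 allows 25 enrolled for 23 analysed. If 9 of 25 are alive at 1 year and the two patients left out are early deaths, 9/25 = 36% (exact 95% CI 18–57%) is reported as 9/23 = 39% (20–61%). The 9 is arbitrary.

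**Model illustration.** Assume exponential survival with median m, and that everyone with the event before L is left out. Then:
- share left out = 1 − 2^(−L/m)
- apparent median = m + L
- 1-year survival 2^(−12/m) is reported as 2^(−(12−L)/m)

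The OS medians of 5.3, 8.6 and 9.3 months and the PFS median of 3.5 months are in Section 1.3. The OS median of 20.1 months (pooled daratumumab monotherapy) and the PFS median of 2.6 months (oral azacitidine combination) are in Section 1.2. Paired results are for L = 35 and 63 days.

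| Endpoint, true median (months) | Left out, of 25 | 1-year rate, true → reported | Apparent median (months) |
|---|---|---|---|
| OS 5.3 | 3.5 / 5.9 | 20.8% → 24.2% / 27.3% | 6.5 / 7.4 |
| OS 8.6 | 2.2 / 3.8 | 38.0% → 41.7% / 44.9% | 9.8 / 10.7 |
| OS 9.3 | 2.1 / 3.6 | 40.9% → 44.5% / 47.7% | 10.5 / 11.4 |
| OS 20.1 | 1.0 / 1.7 | 66.1% → 68.8% / 71.0% | 21.3 / 22.2 |
| PFS 3.5 | 5.1 / 8.4 | 9.3% → 11.7% / 14.0% | 4.7 / 5.6 |
| PFS 2.6 | 6.6 / 10.6 | 4.1% → 5.5% / 7.1% | 3.8 / 4.7 |

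The rise in 1-year OS is 2.7 to 6.9 points. The model covers events inside the window only. It leaves out patients who stop early and die later, whose effect on OS depends on how long they live.

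**Against sampling error.** With 25 exponential times and no censoring, the typical Brookmeyer-Crowley 95% interval (median limits over 4,000 simulations) is about 4.4–14.9 months for a median OS of 8.6, and about 1.8–6.0 for a median PFS of 3.5. The OS shift sits well inside its interval. For PFS, 5.6 months is close to the upper limit.

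**The censoring rule.** In the response-evaluable set, the number of participants without an assessment is zero by definition, so the rule never operates. In a wider set, read literally, it could censor at day 0 a patient who died before any assessment, although the same section counts death as a PFS event. The OS and DOR rules limit censoring to patients without the event; the PFS rule carries no such limit.

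**The case against.** **Intent.** Section 2.2 states the PFS and OS objective for patients treated with the combination, and Section 2.3 times both from first dose, neither with an evaluability condition. The population sentence may have been written with ORR in mind. That is plausible, and the idle censoring rule points the same way for PFS. But Section 8.2 is the operative text and names no other efficacy set, so an analyst following it would leave these patients out. Nor do the documents support inferring that early failures were excluded on purpose.

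**Size.** The background cohorts with medians of 5.3 to 9.3 months had progressed on, or were refractory to, CD38 antibodies. Entry here requires a life expectancy of at least 3 months, longer than the whole 63-day window, and at least 6 months since daratumumab; primary refractoriness to it is excluded. Early deaths are probably fewer than those medians imply. This stands, and the modelled shifts are likely upper values. It does not remove the error: the 20.1-month benchmark still implies 1.0 to 1.7 early deaths of 25.

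**Consequence.** PFS and OS are descriptive, with no test attached, and the OS shift is small beside its interval. This also stands and limits the seriousness. But a wide interval expresses chance error, whereas this error has one direction and a reader of the results could not see it.

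**Stronger readings.** A reader might infer that every early death is lost. Only patients who fail before about week 5 to 9 are; a later death in a patient already in the set is counted. A reader might also infer that the plan orders deaths without an assessment to be censored. Its PFS definition says otherwise, so this is a gap in wording.

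**Conclusion.** The concern holds as a defect in the written plan. PFS and OS are timed from first dose in a set that cannot be entered before about day 63, or about day 35 if starting Cycle 2 counts as receiving it and a baseline or unscheduled assessment counts. The early deaths and early progressions left out can only move the estimates upward, and the PFS censoring rule does not fit the set to which it is attached.

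Under exponential survival and the protocol's background medians, the rise is about 3 to 7 points in 1-year OS and from 3.5 to about 4.7–5.6 months in median PFS. The PFS effect is relatively larger because early progressions are lost as well as deaths. Both figures are illustrations, not forecasts for this population.

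It would be going too far to conclude that the trial's decision is compromised. The go/no-go rule rests on ORR, and changing the PFS and OS set leaves it as it is. The point should be corrected but does not threaten the design.

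**What to change.** In Section 8.2, state:

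- PFS and OS are analysed in every participant given one or more doses of any study drug, counted from that first dose. The response-evaluable set serves only for a sensitivity analysis of these endpoints.
- Any death is a PFS event on the day it occurs. Censoring at first treatment applies only to participants who are alive and have no post-baseline disease assessment.

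Define this all-treated set explicitly. The safety set cannot be borrowed as it stands: Section 7.2 requires at least one dose, whereas Section 8.2 requires at least one cycle.

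The cost is wording. Section 3.5 already follows each subject until 1 year after the last dose, so no extra survival follow-up is needed. The price is slightly less favourable PFS and OS estimates. The sample size and the ORR rule stay as they are.

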2.3 Primary, Secondary, and Exploratory Endpoint(s)

Primary endpoints:

- Rate of overall response (ORR) defined as sCR+CR+VGPR + PR as best response utilizing IMWG Uniform Response Criteria⁵⁵ calculated in the time period from initiation of study treatment until discontinuation of treatment

Secondary Endpoints:

[figure not shown]
- Adverse events, as graded by National Cancer Institute Common Terminology Criteria for Adverse Events (NCI CTCAE version 5.0), assessed from the initiation of study treatment until discontinuation of treatment
- Duration of response (DOR) defined as the duration from the date of initial documentation of a response (PR or better) according to the IMWG criteria to the date of first documented evidence of progressive disease according to the IMWG criteria or death due to PD whichever occurred first.
- Overall survival which is defined from the date of first dose of study treatment to the date of death due to any cause or censored based on the date of last encounter if patient is alive or lost to follow-up.
- Progression-free survival which is defined as the duration from the date of first dose of study treatment to the date of first documented evidence of progressive disease or death, whichever occurs first.
- Change in CD38 surface expression of plasma cells after azacitidine treatment (the CD38 expression of plasma cells pre and post first cycle of azacitidine treatment in this trial will be compared)
- Number of patients who achieve at least 1.5 fold increase in their CD38 expression by flow cytometry after azacitidine treatment
- Correlation of change in CD38 expression after azacitidine treatment to response including depth of response and duration of response

3 Study Design

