5.4 Dose Limiting Toxicity

Dose-limiting toxicities are defined as the following toxicities if they occur anytime within the first 5 weeks of starting azacitidine (anytime within Cycle 1) and are thought to be secondary to azacitidine in combination with daratumumab:

- Grade 4 neutropenia lasting more than 7 days.
- Grade 4 thrombocytopenia lasting more than 7 days despite transfusion support.

- Grade 3 or higher non-hematological toxicity except:
 - Grade 3 nausea, vomiting or diarrhea that can be controlled within 48 hours with maximal supportive care.
 - Grade 3 hyperglycemia that can be controlled within 48 hours with appropriate supportive care.
 - Asymptomatic new Grade 3 or higher electrolyte disturbances that can be controlled with repletion or other medical management within 24 hours.

Severity of AEs will be graded according to CTCAE Version 5.0. As described in [Section 8.2.2](#), interim analysis will occur after accrual of 6 patients in the safety cohort. Study accrual will be stopped until these 6 patients have completed at minimum 5 weeks of treatment after starting azacitidine (ie completed Cycle 1), at which point a formal interim safety analysis will be performed with assessment for DLTs as defined above and safety stopping bounds for DLTs as described in [Section 8.2.2](#). Guidelines for dose reductions of azacitidine due to toxicity or dose delays/holding for daratumumab toxicity are detailed in [Section 5.5](#).

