7.2 Evaluation of Safety

Safety will be measured by adverse events reported to the investigators by participants, laboratory test results, and clinical evaluation. Toxicity will be assessed according to the NCI CTCAE version 5.0. Safety analyses will be performed for all participants who have completed at least one dose of treatment and will encompass the duration of each participant's study treatment and until 30 days after last treatment. Please see [Section 8.1.3](#) for further details on safety analysis.

Any clinically relevant toxicity (\geq grade 3 hematologic adverse events or any grade non-hematologic adverse events) as determined by the treating provider thought to be probably, possibly, or definitely related to daratumumab, azacitidine, or dexamethasone exposure should be reported. Any clinically significant abnormalities persisting at the end of the study/early withdrawal will be followed by the investigator until resolution or until a clinically stable endpoint is reached.

Overview

As the sponsor of the Study, Principal Investigator shall be solely responsible for complying, within the required timelines, any safety reporting obligation to competent Health Authorities, IRB/ECs and any participating (co or sub) investigators, as defined in applicable laws and regulations. For the purposes of this section, safety data includes adverse events, product quality complaints (PQCs), and special situations including pregnancies.

Principal Investigator will provide safety information to Janssen Scientific Affairs, LLC on adverse events, special situations including pregnancies and product quality complaints as defined within this section.

Management of Safety Data

This Study has been designated as an interventional study. As such, all adverse events, special situations including pregnancies and product quality complaints will be reported as described in this exhibit from the time a subject has signed and dated an Informed Consent Form (ICF) until 30 days after the last documented use of a product under study within the study. All subsequent AEs and SAEs will be collected after this period if the Principal Investigator considers the AE/SAE to be causally-related to the use of the study drug.

For the purposes of this study, the J&J medicinal product is: DARZALEX® (daratumumab). The Celgene medicinal product is: VIDAZA™ (azacitidine).

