Adverse events for safety analysis will be monitored for the duration of patient's treatment until 30 days post completion of treatment. The verbatim terms used in the CRF by investigators to identify adverse events will be coded using the Medical Dictionary for Regulatory Activities (MedDRA). Treatment-emergent adverse events are adverse events with onset during the induction/consolidation or maintenance treatment phase or that are a consequence of a pre-existing condition that has worsened since baseline. All reported adverse events will be included in the analysis. For each adverse event, the percentage of subjects who experience at least 1 occurrence of the given event will be summarized.

Summaries, listings, datasets, or subject narratives may be provided, as appropriate, for those subjects who die, who discontinue treatment due to an adverse event, or who experience a severe or a serious adverse event. These will be provided using the same formats as those used for adverse events. At study conclusion frequency, proportion and severity of adverse events, and DLTs by dose level will be tabulated. Point estimates and confidence intervals will be calculated for all dichotomous endpoints.

Efficacy Analysis

Response to study treatment and progressive disease will be evaluated by the IMWG response criteria.⁵⁵

Primary endpoints for efficacy

Primary endpoints for efficacy will be assessed by ORR. See [Section 2.3](#) for definitions. To account for the adaptive nature of Simon's two-stage design, we will calculate the uniformly minimum-variance unbiased estimator, p-value and 95% CI for the response rates. The calculation will be performed using R *clinfun* package (www.r-project.org).

Secondary endpoints for efficacy

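### Section 8.2 restricts AE analyses to patients with at least one cycle, while Section 7.2 uses at least one dose; on a full-cycle reading, patients who leave in the DLT window drop out of the AE tables

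*Combined protocol and SAP*

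**What the plan says.** Two sections define the population for the same safety analyses.

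- Section 8.2 (Analyses Population) bases all AE analyses on "the safety analysis set, which includes all subjects who receive at least 1 cycle of study treatment".
- Section 7.2 states: "Safety analyses will be performed for all participants who have completed at least one dose of treatment". It refers the reader to Section 8.1.3 for details, but Section 8.1 is the sample size section and the table of contents shows no 8.1.3.

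Three other places bear on what one cycle means.

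- The Section 6.1 calendar, footnote a: "Every cycle is 28 days (except for Cycle 1 which extends from day -7 to day 28".
- Section 5.4 counts DLTs occurring "anytime within the first 5 weeks of starting azacitidine (anytime within Cycle 1".
- Section 8.2 (Correlative Studies Analysis) reports the CD38 change "after one cycle of azacitidine treatment". That marrow sample is taken after the first 5-day course and before the first daratumumab dose.

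On which events count, Section 8.2 (Adverse Events) says "All reported adverse events will be included in the analysis", and it also says "Treatment-emergent adverse events are adverse events with onset during the induction/consolidation or maintenance treatment phase", with worsening of pre-existing conditions added. Section 2.3 describes AEs as "assessed from the initiation of study treatment until discontinuation of treatment", while Sections 7.2, 7.6, 8.2 and the calendar continue to 30 days after treatment.

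**The concern.** The two populations differ by exactly the patients who start treatment and leave early. The protocol describes this as the first study of the combination and names toxicity, particularly cytopenias and infections, as the main risk (Section 1.3). Its azacitidine background (Section 1.2) also reports that several reactions, including neutropenia and thrombocytopenia, tend to be more pronounced in the first 1 to 2 cycles.

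Section 8.2 plans a percentage for each AE, with point estimates and confidence intervals for dichotomous endpoints. If the set is limited to patients who got through Cycle 1, those figures are conditional on tolerating the regimen and can understate early severe events. Even without that reading, two analysts could take different denominators from the same document, and the choice could be made after the data are seen.

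**Working it through.** The plan attaches no figure to this point, so there is nothing to reproduce. The check compares the texts and then works through assumed counts.

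**Step 1: length of the excluded period.** On the calendar, Cycle 1 is 7 days before Day 1 plus 28 days from Day 1: 7 + 28 = 35 days, or 5 weeks. Section 5.4 sets the DLT window at the first 5 weeks and equates it with Cycle 1. A full-cycle requirement therefore removes anyone who leaves inside the DLT window.

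**Step 2: effect of each reading of the one-cycle rule.**

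| Reading | Dosed patients excluded |
|---|---|
| Cycle started | Almost none; the sets nearly coincide |
| One azacitidine course (Section 8.2, CD38 text) | Those leaving between Day -7 and Day -3 |
| Full calendar cycle | All who leave between Day -7 and Day 28 |

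No text selects among these.

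**Step 3: formula.** Let N be the number dosed, k the number leaving in Cycle 1, a the leavers with the event and b the others with it.

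- One-dose rate: (a + b)/N
- Full-cycle rate: b/(N − k)

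The full-cycle rate is the lower of the two only when a/k > b/(N − k), that is, when leavers have the event more often than those who stay.

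**Step 4: numbers.** The documents give no Cycle 1 drop-out figure, so k = 1 to 3 is an assumption, with N = 23 from the planned sample size. Intervals are exact (Clopper-Pearson) 95%.

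| Case | One-dose set | Full-cycle set |
|---|---|---|
| Extreme, k = a = 1, b = 0 | 1/23 = 4.3% (0.1–21.9) | 0/22 = 0% (upper 15.4) |
| Extreme, k = a = 3, b = 0 | 3/23 = 13.0% (2.8–33.6) | 0/20 = 0% (upper 16.8) |
| Milder, k = a = 2, b = 2 | 4/23 = 17.4% (5.0–38.8) | 2/21 = 9.5% (1.2–30.4) |
| Opposite, k = 2, a = 0, b = 2 | 2/23 = 8.7% (1.1–28.0) | 2/21 = 9.5% (1.2–30.4) |

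**Step 5: alternative base.** Section 8.1 caps accrual at 25 to allow for about 10% drop-out or ineligibility. With 25 dosed and 2 leaving, assumed all in Cycle 1, the milder case is 4/25 = 16.0% against 2/23 = 8.7%, and the extreme case is 2/25 = 8.0% against 0/23. The milder case shifts by about the same amount as with N = 23.

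**Step 6: what is not affected.** Table 8-1 counts DLTs per number of subjects and is not tied to the safety analysis set, so the DLT boundary does not inherit this problem.

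**Step 7: wording around treatment emergence.** The calendar heads Day -7 to Day -3 as a pre-induction phase, which the treatment-emergent definition does not name. Because all reported AEs enter the analysis, this touches only the treatment-emergent label. The earlier end point in Section 2.3 likewise affects only the stated window.

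**The case against.** The best counter-argument is that the harm needs the full-cycle reading, and other text points away from it. Section 8.2 speaks of patients having completed Cycle 1 when it describes the lead-in, so a different verb for the safety set may mean a different thing, and the CD38 text uses a cycle of azacitidine for one 5-day course. This stands as a limit: the conflict between the sections is certain, while the bias is conditional. Against it, the preceding sentence in Section 8.2 requires 2 cycles received for the response-evaluable set, where cycles delivered is the natural sense.

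Second, the statement that all reported AEs are included might keep early leavers in the numerator. It makes their loss less certain, but it names no population and so leaves the denominator open.

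Third, early severe events are seen elsewhere: any death is an SAE, Grade 3–5 AEs are reviewed monthly, and the DSMC reviews SAEs. That protects patients during the trial. It does not repair the AE tables, and narratives are only something that may be provided.

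Fourth, 3 leavers of 23 (13%) in Cycle 1 alone exceeds the plan's only drop-out allowance of about 10%, which covers ineligibility and drop-out at any time. This is fair, and the 13.0%-to-0% case should be read as an outer bound. The calculation on a base of 25 gives a similar shift in the milder case.

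Fifth, the protocol's hold-and-resume and dose-delay rules would reduce Cycle 1 departures. That is plausible, but routes out remain, among them death, withdrawal and permanent discontinuation after a Grade 4 injection-related reaction.

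**Conclusion.** The concern holds. Sections 7.2 and 8.2 give different entry rules for the same safety analyses, neither is stated to govern, and the cross-reference that might settle it leads nowhere. Confidence in the contradiction is high.

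The size of any bias rests on two assumptions: that one cycle means the full calendar cycle, and that 1 to 3 of about 23 patients leave in Cycle 1. Under these, an event rate in the high teens could be roughly halved when early leavers carry the event, and an event confined to early leavers would vanish from the tables. If early leavers are free of the event, the rate moves slightly upward instead. The primary endpoint, the Simon rule and DLT monitoring are untouched. This should be fixed before analysis, but it does not undermine the design.

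**What to change.** In Section 8.2, define the safety analysis set as all subjects who receive at least one dose of any study drug, which brings it into line with Section 7.2. Correct the pointer to Section 8.1.3 in Section 7.2 so that it leads to the safety analysis text in Section 8.2.

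As a wording alignment, define treatment-emergent as onset or worsening from the first azacitidine dose (Cycle 1 Day -7) to 30 days after the last dose of study treatment, and give the AE endpoint in Section 2.3 the same end point.

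The cost is wording only. AEs are already collected from consent to 30 days after the last dose, and the sample size, the Simon rule and the DLT boundary do not change.
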